8.2.2 Physical examinations

Physical examinations will be performed according to the assessment schedules (see the SoAs). Full physical examinations will include assessments of the head, eyes, ears, nose, and throat and the respiratory, cardiovascular, gastrointestinal, urogenital, musculoskeletal, neurological, dermatological, hematologic/lymphatic, and endocrine systems. Height will be measured at part II screening only. Targeted physical examinations are to be utilised by the Investigator on the basis of clinical observations and symptomatology. Situations in which physical examination results should be reported as AEs are described in Section 8.3.7.

8.2.3 Vital signs

Vital signs (blood pressure [BP], pulse, temperature, and respiration rate) will be evaluated according to the SoAs. WT is also recorded at each visit along with vital signs.

First infusion

On the first infusion day, participants will be monitored and vital signs collected/recorded in eCRF prior to, during, and after infusion of IP as presented in the bulleted list below.

BP and pulse will be collected from participants before, during, and after each infusion at the following times (based on a 60-minute infusion):

- Prior to the beginning of the infusion (measured once from approximately 30 minutes before up to 0 minutes [ie, the beginning of the infusion])
- Approximately 30 minutes during the infusion (halfway through infusion)
- At the end of the infusion (approximately 60 minutes ± 5 minutes)

If the infusion takes longer than 60 minutes, then BP and pulse measurements should follow the principles as described above or be taken more frequently if clinically indicated. A 1-hour observation period is recommended after the first infusion of durvalumab.

Subsequent infusions

BP, pulse, and other vital signs should be measured and collected/recorded in the eCRF prior to the start of the infusion. Participants should be carefully monitored, and BP and other vital signs should be measured during and post infusion as per institution standard and as clinically indicated. Any clinically significant changes in vital signs should be entered onto an unscheduled vital signs CRF page.

Situations in which vital signs results should be reported as AEs are described in Section 8.3.7. For any AEs of infusion reactions, the vital signs values should be entered into the CRF.

8.2.4 Electrocardiograms

Resting 12-lead ECGs will be recorded at part II screening and as clinically indicated throughout the study (see the SoAs). ECGs should be obtained after the participant has been in a supine position for 5 minutes and recorded while the participant remains in that position.

In case of clinically significant ECG abnormalities, including a QT interval corrected for heart rate using Fridericia's formula (QTcF) value >470 ms, 2 additional 12-lead ECGs should be obtained over a brief period (eg, 30 minutes) to confirm the finding.

Situations in which ECG results should be reported as AEs are described in Section 8.3.7.

8.2.5 WHO/ECOG performance status

WHO/Eastern Cooperative Oncology Group (ECOG) PS will be assessed at the times specified in the assessment schedules (see the SoAs) based on the following:

- 1 Fully active; able to carry out all usual activities without restrictions
- 2 Restricted in strenuous activity, but ambulatory and able to carry out light work or work of a sedentary nature (eg, light housework or office work)
- 3 Ambulatory and capable of self-care, but unable to carry out any work activities; up and about more than 50% of waking hours
- 4 Capable of only limited self-care; confined to bed or chair more than 50% of waking hours
- 5 Completely disabled; unable to carry out any self-care and totally confined to bed or chair
- 6 Dead

Any significant change from Baseline or part II screening must be reported as an AE.

WHO/ECOG PS should also be collected at other study site visits that the participant attends, if appropriate study site staff are available to collect such information. In addition, WHO/ECOG PS should be provided when information on subsequent anticancer therapy is provided, where possible.

8.2.6 Other safety assessments

If new or worsening pulmonary symptoms (e.g. dyspnoea) or radiological abnormality suggestive of pneumonitis/interstitial lung disease (ILD) is observed, toxicity management as described in detail in the Dosing Modification and Toxicity Management Guidelines (see Section 8.4.5) will be applied. The results of the full diagnostic workup (including high-resolution computed tomography [HRCT], blood and sputum culture, haematological parameters, etc) will be captured in the eCRF. It is strongly recommended to perform a full diagnostic workup to exclude alternative causes such as lymphangitic carcinomatosis, infection, allergy, cardiogenic oedema, or pulmonary haemorrhage. In the presence of confirmatory HRCT scans where other causes of respiratory symptoms have been excluded, a diagnosis of pneumonitis (ILD) should be considered and the Dosing Modification and Toxicity Management Guidelines should be followed.

Pneumonitis (ILD) investigation

The following assessments, and additional assessments if required, will be performed to enhance the investigation and diagnosis of potential cases of pneumonitis. The results of the assessment will be collected.

- Physical examination
 - Signs and symptoms (cough, shortness of breath, and pyrexia, etc) including auscultation for lung field
- Saturation of peripheral oxygen (SpO₂)
- Other items
 - When pneumonitis (ILD) is suspected during study treatment, the following markers should be measured where possible:
 - $\circ~$ ILD Markers (KL-6 and surfactant-associated protein) and $\beta\text{-D-glucan}$
 - Tumour markers: Particular tumour markers that are related to disease progression
 - Additional Clinical chemistry: C-reactive protein, lactate dehydrogenase

8.3 Collection of adverse events

The Principal Investigator is responsible for ensuring that all staff involved in the study are familiar with the content of this section.

The definitions of an AE or SAE can be found in Appendix B.

AEs will be reported by the participant (or, when appropriate, by a caregiver, surrogate, or the participant's legally authorised representative).

The Investigator and any designees are responsible for detecting, documenting, and recording events that meet the definition of an AE or SAE. For information on how to follow up AEs, see Section 8.3.3.

8.3.1 Method of detecting adverse events and serious adverse events

Care will be taken not to introduce bias when detecting AEs and/or SAEs. Open-ended and non-leading verbal questioning of the participant is the preferred method to inquire about AE occurrences.

8.3.2 Time period and frequency for collecting adverse event and serious adverse event information

AEs and SAEs will be collected from the time of the participant signing the ICF of study procedure (part II screening) until the Follow-up Period is completed (90 days after the last dose of study drug). If an event that starts post the defined safety Follow-up Period noted above is considered to be due to a late onset toxicity to study drug, then it should be reported as an AE or SAE as applicable.

All SAEs will be recorded and reported to the Sponsor or designee within 24 hours, as indicated in Appendix B. The Investigator will submit any updated SAE data to the Sponsor within 24 hours of it being available.

Investigators are not obligated to actively seek AEs or SAEs in former study participants. However, if the Investigator learns of any SAE, including a death, at any time after a participant's last visit and he/she considers the event to be reasonably related to the study treatment or study participation, the Investigator should notify the Sponsor.

The method of recording, evaluating, and assessing causality of AE and SAE and the procedures for completing and transmitting SAE reports are provided in Appendix B.

8.3.3 Follow-up of adverse events and serious adverse events

After the initial AE/SAE report, the Investigator is required to proactively follow each participant at subsequent visits/contacts. All AEs and SAEs will be followed until resolution, stabilisation, the event is otherwise explained, or the participant is lost to follow-up.

Any AEs that are unresolved at the participant's last visit in the study are followed up by the Investigator for as long as medically indicated (this may be beyond the 90 days after the last dose of durvalumab), but without further recording in the eCRF. AstraZeneca retains the right

to request additional information for any participant with ongoing AE(s)/SAE(s) at the end of the study, if judged necessary.

8.3.4 Adverse event data collection

The following variables will be collected for each AE:

- AE (verbatim)
- The date when the AE started and stopped
- The maximum CTCAE grade reported
- Changes in CTCAE grade (report only the maximum CTCAE grade for a calendar day)
- Whether the AE is serious or not
- Investigator causality rating against the IPs (yes or no)
- Action taken with regard to IPs
- Administration of treatment for the AE
- Outcome

In addition, the following variables will be collected for SAEs:

- Date the AE met criteria for SAE
- Date the Investigator became aware of the SAE
- Seriousness criteria
- Date of hospitalisation
- Date of discharge
- Probable cause of death
- Date of death
- Whether an autopsy was performed
- Causality assessment in relation to study procedure(s)
- Causality assessment in relation to other medication, as explained in Section 8.3.5
- Description of the SAE

The grading scales found in the revised NCI CTCAE version 5.0 will be utilised for all events with an assigned CTCAE grading. For those events without assigned CTCAE grades, the recommendation in the CTCAE criteria that converts mild, moderate, and severe events into CTCAE grades should be used. A copy of the CTCAE version 5.0 can be downloaded from the Cancer Therapy Evaluation Program website (http://ctep.cancer.gov).

Any non-serious AE that is ongoing at the time of the final DCO is to be followed up at the discretion of the Investigator, per local practice, and in alignment with the toxicity

management guidelines (refer to Section 8.4.5) of this protocol. Data will not be captured for the purposes of this study outside of being recorded in the participants' source documents.

8.3.5 Causality collection

The Investigator will assess causal relationship between IP and each AE, and answer "yes" or "no" to the question, "Do you consider that there is a reasonable possibility that the event may have been caused by the investigational product?"

For SAEs, causal relationship will also be assessed for other medication and study procedures. Note that for SAEs that could be associated with any study procedure, the causal relationship is implied as "yes."

A guide to the interpretation of the causality question is found in Appendix B.

8.3.6 Adverse events based on signs and symptoms

All AEs spontaneously reported by the participant or reported in response to the open question from the study site staff, "Have you had any health problems since the previous visit/you were last asked?" or revealed by observation will be collected and recorded in the eCRF. When collecting AEs, the recording of diagnoses is preferred (when possible) to recording a list of signs and symptoms. However, if a diagnosis is known and there are other signs or symptoms that are not generally part of the diagnosis, the diagnosis and each sign or symptom will be recorded separately.

8.3.7 Adverse events based on examinations and tests

The results from protocol-mandated laboratory tests and vital signs will be summarised in the Clinical Study Report (CSR). Deterioration as compared to Baseline in protocol-mandated laboratory values and vital signs should therefore only be reported as AEs if they fulfil any of the SAE criteria or are the reason for discontinuation of treatment with the IP.

If deterioration in a laboratory value/vital sign is associated with clinical signs and symptoms, the sign or symptom will be reported as an AE and the associated laboratory result/vital sign will be considered as additional information. Wherever possible, the reporting Investigator uses the clinical rather than the laboratory term (eg, anaemia versus low haemoglobin value). In the absence of clinical signs or symptoms, clinically relevant deteriorations in non-mandated parameters should be reported as AE(s).

Asymptomatic Grade 3 or 4 increases in amylase or lipase resulting in interruption of dosing (refer to Section 8.4.5) should be reported as AEs.

Deterioration of a laboratory value that is unequivocally due to disease progression should not be reported as an AE/SAE.

Any new or aggravated clinically relevant abnormal medical finding at a physical examination as compared with the baseline assessment will be reported as an AE unless unequivocally related to the disease under study; see Section 8.3.8 and Section 8.3.9.

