8.3.13 Adverse events of special interest

An adverse event of special interest (AESI) is one of scientific and medical interest specific to understanding of the IP and may require close monitoring. An AESI may be serious or non-serious. The rapid reporting of AESIs allows ongoing surveillance of these events in order to characterise and understand them in association with the use of this IP.

AESIs for durvalumab include but are not limited to events with a potential inflammatory or immune-mediated mechanism and which may require more frequent monitoring and/or interventions such as steroids, immunosuppressants, and/or hormone replacement therapy. These AESIs are being closely monitored in clinical studies with durvalumab monotherapy and combination therapy. An imAE is defined as an AESI that is associated with drug exposure and is consistent with an immune-mediated mechanism of action and where there is no clear alternate aetiology. Serologic, immunologic, and histologic (biopsy) data, as appropriate, should be used to support an imAE diagnosis. Appropriate efforts should be made to rule out neoplastic, infectious, metabolic, toxin, or other etiologic causes of the imAE.

If the Investigator has any questions in regards to an event being an imAE, the Investigator should promptly contact the Study Physician.

AESIs/imAEs observed with anti PD-1/PD-L1 agents such as durvalumab include:

- Diarrhoea/colitis and intestinal perforation
- Pneumonitis/ILD
- Endocrinopathies (ie, events of hypophysitis/hypopituitarism, adrenal insufficiency, hyper- and hypo-thyroidism, and type I diabetes mellitus)
- Hepatitis/transaminase increases

- Nephritis/blood creatinine increases
- Pancreatitis/serum lipase and amylase increases
- Rash/dermatitis
- Myocarditis
- Myositis/polymyositis
- Other inflammatory responses that are rare/less frequent with a potential immunemediated aetiology include, but are not limited to, haematological events, neuropathy/neuromuscular toxicity (eg, Guillain-Barré and myasthenia gravis), noninfectious encephalitis, non-infectious meningitis, pericarditis, rheumatological events, sarcoidosis, skin events, uvetitis [and other events involving the eye] and vasculitis.

In addition, infusion-related reactions and hypersensitivity/anaphylactic reactions with a different underlying pharmacological aetiology are also considered AESIs.

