Pneumonitis, Hepatic events, Diarrhea/Colitis, Intestinal perforations, Adrenal Insufficiency, Type 1 diabetes mellitus, Hyperthyroid events, Hypophysitis, Hypothyroid events, Thyroiditis, Renal events, Dermatitis/Rash, Pancreatic events, Myocarditis, Myasthenia gravis, Guillain-Barre syndrome, Myositis, Infusion/hypersensitivity reactions, Other rare/miscellaneous. Other categories may be added or existing terms may be merged as necessary. An AstraZeneca medically qualified expert after consultation with the Global Patient Safety Physician has reviewed the AEs of interest and identified which preferred terms contribute to each AESI/AEPI. A further review will take place prior to Database lock (DBL) to ensure any further terms not already included are captured within the categories.

Immune-mediated Adverse Events (imAEs)

imAEs will be identified from both AEs of special interest (AESIs) and AEs of possible interest (AEPIs) based on programmatic rules that consider interventions involving systemic steroid therapy, immunosuppressant use, and/or endocrine therapy (which, in the case of AEPIs, occurs after first considering an Investigator’s causality assessment and/or an

Investigator's designation of an event as immune-mediated). Endocrine therapies include standard endocrine supplementation, as well as treatment of symptoms resulting from endocrine disorders (for example, therapies for hyperthyroidism include beta blockers [e.g., propranolol], calcium channel blockers [e.g., verapamil, diltiazem], methimazole, propylthiouracil, and sodium perchlorate). Further details are provided in the imAE charter.

In addition, the Sponsor may perform medical review of those AESIs and classify them as imAEs or not imAEs via an independent manual adjudication process.

Confirmed/Suspected COVID-19 infection

Confirmed/suspected COVID-19 infection is defined as an AE with preferred term within the AE search criteria developed by the latest MedDRA MSSO guidance for COVID-19.

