 - AE onset prior to subsequent therapy. Which includes AEs with an onset date (or pre-treatment AEs that increase in severity) on or after the date of first dose and up to and including 90 days following the last dose of study medication (durvalumab/placebo), or AE start date \leq the date of initiation of the first subsequent therapy (whichever occurs first).
- Death after end of safety follow up period (last dose of study medication (durvalumab/placebo) + 90 days) and not due to disease under investigation
- COVID-19 related death
- Unknown reason for death
- Other deaths

This summary will be repeated for all deaths on-treatment or within 90 days of last dose of durvalumab/placebo.

Adverse events of special interest and possible interest

Preferred terms used to identify adverse events of special interest and possible interest (as defined in [section 3.3.1](#)) will be listed before DBL and documented in the Study Master File. Grouped summary tables of certain MedDRA preferred terms will be produced and may also show the individual preferred terms which constitute each AESI/AEPI grouping. Groupings will be based on preferred terms provided by the medical team prior to DBL, and a listing of the preferred terms in each grouping will be provided.

An overall summary will include the number and percentage of patients with:

- Any AESI/AEPI (*)
- Any AESI/AEPI, causally related to durvalumab/placebo (*)
- Any AESI/AEPI of CTCAE grade 3 or 4
- Any AESI/AEPI of CTCAE grade 3 or 4, causally related to durvalumab/placebo
- Any AESI/AEPI with outcome of death
- Any AESI/AEPI with outcome of death, causally related to durvalumab/placebo

- Any serious AESI/AEPI (*)
- Any serious AESI/AEPI, causally related to durvalumab/placebo
- Any AESI/AEPI leading to discontinuation of durvalumab/placebo (*)
- Any AESI/AEPI leading to discontinuation of durvalumab/placebo, causally related to durvalumab/placebo
- Any AESI/AEPI leading to dose delay of durvalumab/placebo
- Any AESI/AEPI leading to concomitant medication (*)
- Any AESI/AEPI leading to concomitant medication use (steroids) (*)
- Any AESI/AEPI leading to concomitant medication use (high dose steroids) (*)
- Any AESI/AEPI leading to concomitant medication use (endocrine therapy) (*)
- Any AESI/AEPI leading to concomitant medication use (other immunosuppressants) (*)

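### Protocol 8.3.7 conflicts with 8.3.13: a symptom-free, non-serious laboratory event that delays dosing or is treated need not have an AE record, so it can miss the AESI, imAE and dose-delay tables

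*Protocol*

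**What the plan says.** Protocol 8.3.7 sets a restrictive rule for laboratory tests and vital signs that the protocol requires. Because the results will be tabulated in the CSR anyway, deteriorations in required "laboratory values and vital signs should therefore only be reported as AEs if they fulfil any of the SAE criteria". The other general trigger is that the deterioration led to IP being stopped. The section then adds three provisions:

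- "Asymptomatic Grade 3 or 4 increases in amylase or lipase resulting in interruption of dosing" are to be reported as AEs.
- If a deterioration comes with signs or symptoms, "the sign or symptom will be reported as an AE and the associated laboratory result/vital sign will be considered as additional information".
- Clinically relevant deteriorations in tests that are not mandated are reportable even without symptoms.

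Protocol 8.3.13 lists the AESIs and imAEs expected with this class. The list includes "Hepatitis/transaminase increases", the corresponding renal entry for creatinine, the pancreatic entry for lipase and amylase, and hyper- and hypothyroidism. It states that an AESI can be non-serious.

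The SAP builds on AE records. In SAP 3.3.1, AESIs and AEPIs are defined as AEs, and "imAEs will be identified from both AEs of special interest (AESIs) and AEs of possible interest (AEPIs) based on programmatic rules" that look at steroid, immunosuppressant and endocrine treatment. SAP 4.2.5.1 tabulates AEs that led to a dose delay and, in the AESI/AEPI overview, "Any AESI/AEPI leading to dose delay of durvalumab/placebo".

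**The concern.** The two protocol sections give a site different answers for the same event. Under 8.3.7, a symptom-free, non-serious ALT rise that delays the next infusion is not an AE. Under 8.3.13 it is an AESI. Sites may therefore record identical events differently, and the safety tables would partly reflect which section a site followed.

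Immune-mediated toxicity is the main identified risk of this drug. The imAE algorithm is designed to find events that needed a steroid, an immunosuppressant or endocrine therapy, but it can only search events that already have an AE record. Laboratory-only toxicity that was managed while treatment continued is exactly what 8.3.7 can leave unrecorded.

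**Working it through.** No plan figure bears on this point, so the check is a trace of one event through the documents.

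**1. Are the tests mandated?**
- ALT/AST: yes. Clinical chemistry is scheduled at every cycle in Protocol Table 1, and its footnote m requires liver function results before each infusion.
- TSH: yes. It is scheduled at every cycle in Table 1.
- Creatinine: mixed. Footnote m of Table 1 requires it before each infusion. Footnote d of Table 7 is attached to creatinine and limits creatinine clearance testing to baseline, Day 1 and clinical need. If a later test counts as non-mandated, a clinically relevant deterioration is reportable.

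**2. Apply 8.3.7.** Take a participant with a symptom-free, non-serious ALT/AST rise and no diagnosis recorded. A dose is delayed or a steroid is started, and IP later resumes.
- SAE criterion met: no, by construction.
- Reason for stopping IP: no.
- Sign or symptom present: no.
- Amylase or lipase: no.
- Non-mandated test: no.

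Result: no AE is due. If the same participant had a Grade 3 lipase rise that interrupted dosing, an AE would be due. The protocol gives no reason for the difference, although both tests are in Table 7 and both have an entry in the 8.3.13 list.

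**3. Apply the other sections to the same participant.**
- 8.3.13: the event is a listed AESI, and non-serious events count.
- Section 1.1: a dose delay under the toxicity guidelines is described as due to an AE.
- Table 5 in 6.4: one of the allowed uses of immunosuppressive medication during treatment is the management of treatment-related AEs.

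Result: an AE is presupposed. This contradicts step 2.

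**4. Follow the step 2 result into the SAP.** With no AE record there is no AESI or AEPI, and so no imAE. There is also no entry in the dose-delay AE table or the matching AESI/AEPI row. The Sponsor's optional manual review in SAP 3.3.1 covers AESIs only, so it would not find the event either. Causality, action taken with IP and treatment given are collected per AE (Protocol 8.3.4), so these are not captured for the event.

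**5. What is still reported?**
- SAP 4.2.5.2: CTCAE shift tables that include ALT, AST and creatinine; ALT/AST bands; TSH summaries; creatinine clearance categories.
- SAP 4.2.12: reasons for dose delays and interruptions.
- In the database: dose delays (Protocol 6.3) and concomitant medication with its reason for use (Protocol 6.4).

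No planned output joins the laboratory event to the delay or the treatment.

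**6. Size.** The documents give no incidence, so no estimate is possible. For scale only: 2/3 × 400 ≈ 267 participants are planned for durvalumab, and 1% of 267 is about 2.7 participants. This converts a rate to a count if a rate becomes known.

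**The case against.** The strongest reply is that few events fall through. Symptomatic events are reportable. Protocol 8.3.6 prefers diagnoses, and 8.3.7 prefers the clinical to the laboratory term, so hepatitis, nephritis or hypothyroidism would be recorded. The thyroid AESI is itself a diagnosis, and a participant started on thyroid hormone would ordinarily have one. Liver cases that meet Hy's law are handled as SAEs under 8.3.8. These points stand. A reader might infer that transaminase, creatinine and thyroid toxicity in general disappears from the AE tables unless it ends treatment. The documents do not support that. The gap is confined to laboratory-only events with no symptom and no recorded diagnosis.

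A second reply is that delays and steroids are framed as AE management, so a site taking those steps already has an AE in mind. This shows what the authors probably intended, but it does not settle the matter: 8.3.7 uses the word only, and nothing says that 8.3.13 overrides it. The framing adds to the conflict.

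A third reply is that the laboratory tables and the reasons for delay still appear. That is true, and it means that the values themselves are not lost. What is lost is the link to causality, delay and treatment that the imAE tables are meant to show.

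A fourth reply is that changing the rule at protocol version 6.0 creates two reporting standards within one trial. This is a fair warning. It is why the query in the fix must cover all participants in both arms.

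**Conclusion.** The point holds in a limited form. Sections 8.3.7 and 8.3.13 conflict. Followed literally, 8.3.7 allows a symptom-free, non-serious, laboratory-only event that was managed by dose delay or by steroid, immunosuppressant or endocrine treatment to go without an AE record. It would then be missing from the AESI/AEPI, imAE and AE dose-delay tables. This is firm for ALT/AST, less clear for creatinine, and for TSH depends on no thyroid diagnosis having been recorded.

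The number of events affected cannot be estimated. A reader might infer a specific undercount, or one mainly on durvalumab. The second is plausible, since these are listed effects of the class, but the documents give no rate in either arm and show neither.

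Two assumptions remain open. Appendix B (SAE definitions), the toxicity management guidelines and the imAE charter were not available for this review, so some treated cases may qualify as SAEs or be covered there. Sites may also already be recording these events in line with 8.3.13. Neither possibility removes the need to reconcile the text.

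**What to change.** Reconcile 8.3.7 with 8.3.13 by widening the existing amylase/lipase exception. Besides the current triggers, a deterioration in a mandated laboratory value would be recorded as an AE if any of these applies:

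- it leads to delay or interruption of IP;
- it is treated with a steroid, an immunosuppressant or endocrine therapy;
- the Investigator judges it to be an AESI or imAE.

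The same edit should make clear whether on-treatment creatinine is a mandated test, since Table 1 footnote m and Table 7 footnote d point in different directions.

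Then run a blinded query over all participants in both arms for dose delays or concomitant medications whose recorded reason is a laboratory abnormality and for which there is no matching AE. It should be finished before the database lock for the final PFS analysis, because SAP 5.1 has the study unblinded at that point. The query applies one ascertainment rule to the whole trial and uses data already collected under Protocol 6.3 and 6.4.

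The cost is a sentence or two in the protocol or a memo to sites, some query work, and a modest rise in reported AE counts. Only AE recording changes; when to delay a dose or give treatment is untouched.
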